\* Targeted physical examination will be performed at screening. If needed, targeted physical examination based on medical history and Investigator’s discretion might be performed at V01.

† Female participants of childbearing potential must have a negative urine pregnancy test prior to administration of study product. Urine pregnancy test is applicable to childbearing potential female participant (to be considered of non-childbearing potential, a female must be post-menopausal for at least 1 year or surgically sterile). Urine pregnancy test is to be performed at screening (performed within -D04 and -D01) and before vaccinations.

‡ Safety laboratory assessments will include: serum chemistries (including liver enzymes and renal function); hematology (complete blood count with differential) and coagulation times (PT and PTT); urinalysis; Microscopy will be performed if urinalysis is abnormal. In cases of abnormal safety laboratory results, unscheduled visits may occur and laboratory tests may be checked based on Investigator’s judgment. Assessment of clinical safety laboratory parameters at screening must be performed within -D04 to -D01.

§ If a participant seeks an authorized/approved COVID-19 vaccine, they will be invited to an unscheduled visit prior to receiving the vaccine and requested to provide a blood sample for serological assessment (UB0001).

\*\* BL0001 will be collected at pre-vaccination (baseline). BL0002 sample will be collected prior to D22 vaccination.

†† Result of point-of-care SARS-CoV-2 antibody test must be obtained within -D04 to -D01.

Assessment of clinical safety laboratory parameters must be performed within -D04 to -D01.

Screening activities like COVID-19 antibody test and blood and urine sampling for safety tests may be performed on the day of enrollment as long as the results to assess exclusion criteria are available prior to enrollment.

Testing of HIV antibody, Hepatitis B surface antigen, Hepatitis B core antibody, and Hepatitis C antibody must be obtained within -D08 to -D01. This testing will be performed at the study center using local accepted diagnostic tests. It is to be noted that results for the above-mentioned HIV and Hepatitis serology tests obtained outside the study within 4 weeks prior to V01 will be accepted.

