3.1 Trial Design

This is a Phase I/II, first-in-human, multi-center, safety and immunogenicity study comprised of 2 sequential cohorts: a lead-in, open-label, dose escalation Sentinel Cohort (initial target of 25 participants) with Complete Sentinel Early Safety Data Reviews (CS-ESDRs), followed by a

randomized, modified double-blind, dose-ranging, placebo-controlled Full Enrollment Cohort (initial target of 308 participants, but actual number could be lower as it will be determined by dose-levels progressing after CS-ESDR), to evaluate the safety and immunogenicity of the SARS-CoV-2 mRNA vaccine in healthy adult participants (18 years of age and older) in the US and Honduras.

Participants in the Initial Sentinel Cohort were 18-49 years of age at enrollment and were assigned to receive 2 injections of one of the 3 dose-levels (ultra-low-dose [■] µg], low-dose [■] µg] and medium-dose [■] µg]) of the study vaccine, 21 days apart, in a stepwise open-label manner. In case an alert threshold was met in a dose-level group in the Initial Sentinel Cohort, the corresponding dose-level group could be expanded to reach a total of approximately 25 participants as shown in Figure 1.5 of the protocol. Details of the planned safety parameters and alert thresholds to be examined for the Sentinel Cohort safety analysis are provided in Section 8.4.1 and Section 8.4.2 of the protocol. The Full Enrollment Cohort includes both Cohort 1 and Cohort 2. Participants in Cohort 1 of the Full Enrollment Cohort (hereafter referred to as Cohort 1) were to receive a single injection of study intervention while participants in Cohort 2 of the Full Enrollment Cohort (hereafter referred to as Cohort 2) were to receive 2 vaccinations (to be given 21 days apart), of one of the study interventions (ultra-low-dose [■] µg], low-dose [■] µg], medium-dose [■] µg], or placebo). Halting rules for the Entire Study are provided in Section 8.4.3 of the protocol.

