5.1 Statistical Methods

Safety, immunogenicity, and efficacy analysis will be undertaken including those data collected before the date of receiving an authorized/approved COVID-19 vaccine. Those data collected on or after receiving an authorized/approved COVID-19 vaccine will be listed separately.

For those participants who did not receive an authorized/approved COVID-19 vaccine outside the study, immunogenicity data collected until the last scheduled/unscheduled study visit will be used for analysis. Rules about how to handle unscheduled visit are detailed in Table 5.2. Safety data collected until the last phone contact will be used for analysis if participants did not receive an authorized/approved COVID-19 vaccine outside the study

Safety analyses will be conducted based on two populations: *i*) participants in the Full Enrollment Cohort (Cohort 1 and 2) only, and *ii*) all participants in the Full Enrollment Cohort and Sentinel Cohort, if necessary. Immunogenicity analyses and efficacy analyses will be conducted based on the combined population (Full Enrollment Cohort + Sentinel Cohort) only, in which the same

dose-level group in Sentinel Cohort and Full Enrollment Cohort will be pooled. Subgroup analyses will be performed by age-group.

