5.1.1.2 Statistical Methods for Primary Safety Objective

The following safety parameters will be used for the evaluation of safety. Additional parameters may be displayed as appropriate.

Solicited Reactions

Number and percentage of participants with:

- Presence of solicited injection site reactions and systemic reactions occurring up to 7 days after injection
- Each solicited reaction according to time of onset, maximum intensity, and number of days of occurrence over the solicited period

Unsolicited Events and Reactions

Number and percentage of participants with:

- Any unsolicited immediate systemic event in the 30 minutes after injection
- Any unsolicited event and reaction (using the current MedDRA version) 21 days after injection
- Any unsolicited event/reaction according to time of onset, maximum intensity, and duration

SAEs

Number and percentage of participants with:

- Any SAE within 21 days after injection and throughout the entire study according to SOC and PT, seriousness, and outcome

AESIs

Number and percentage of participants with:

- Any AESI within 21 days after injection and throughout the entire study according to SOC and PT, seriousness, and outcome

MAAEs

Number and percentage of participants with:

- Presence of MAAEs within 21 days after injection and throughout the entire study

Laboratory tests

- Presence of out-of-range biological test results up to 8 days post-last dose (ie, up to D09 for Cohort 1 and up to D30 for Sentinel Cohort and Cohort 2)
- Summary of toxicity grade shift from baseline

For descriptive purposes, the statistics presented in [Table 5.1](#) will be produced for the above safety parameters for each intervention group and each age group. The same dose-level group in Sentinel Cohort and Cohort 2 will also be pooled for analysis.

Harm analysis

Harm analysis assessed based on split of COVID-19 case will be assessed based on Safety Analysis Set (SafAS) at the time of the final analysis. Participants will be analyzed according to the study intervention they received. For the assessment, all dose-level arms will be pooled, and all placebo arms will be pooled as well.

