5.1.1.4 Statistical Methods for Primary Immunogenicity Objective

The primary endpoints for the evaluation of immunogenicity are based on pseudovirus neutralizing antibody titers against D614 variant, which will be measured with the pseudovirus neutralization assay. The statistical analyses will be performed for the following primary endpoints below in each age and intervention group:

1. Neutralizing antibody titer on D01, D22, and D36
2. Fold-rise (fold-rise in serum antibody neutralization titer post-vaccination relative to D01) at D22, and D36
3. 2-fold and 4-fold rise in serum neutralization titer relative to D01 at D22, and D36
4. Occurrence of neutralizing antibody seroconversion, defined as baseline values below LLOQ with detectable neutralization titer above assay LLOQ at D22 and D36

The 95% CIs for the geometric mean titers (GMTs)/geometric mean concentrations (GMCs) and GMT ratios will be calculated using normal approximation of log-transformed titers. The 95% CIs for the proportions will be based on the Clopper-Pearson method. Additional parameters may be displayed as appropriate.

For descriptive purposes, the statistics presented in [Table 5.1](#) will be produced for each intervention group and each age group. The same dose-level group in Sentinel Cohort and Cohort 2 will be pooled for analysis.

Additionally, to evaluate independent determinants of primary immunogenicity endpoints, regression models may be constructed for log transformed titers and occurrence of 4-fold rise in serum neutralization titer relative to D01 at D22 for Cohort 1 and D36 for Sentinel Cohort and Cohort 2. When the outcome/dependent variable is a continuous numerical variable, linear model may be utilized; when the outcome/dependent variable is a categorical variable, logistic regression models may be utilized. Explanatory/independent variables inserted in these models would include age group (18-49 years, ≥ 50 years) and the injection schedule (1-injection, 2-injections). Models evaluating antibody titers or rates may include also an explanatory variable corresponding to the antigen dose level (ultra-low-dose, low-dose, medium-dose) when more than 1 dose level is to be used for the Full enrollment Cohort. Multiplicative interaction terms will be included in expanded models to assess for evidence of effect modification. Non-significant interaction terms with critical value < 0.05 can be removed from the models.

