5.2.5 Populations Used in Analyses

Participants' disposition, demographics, baseline characteristics and exposure will be summarized by planned intervention group for all screened participants or Enrolled participants.

The primary safety analysis will be performed on the SafAS, SafAS1, and SafAS2 by injection group according to the vaccine received.

The primary immunogenicity analyses, the secondary immunogenicity analyses, and the exploratory immunogenicity analyses will be performed on the mFAS by injection group as actually received. This is due to a high rate of protocol deviations and dosing errors found in the preliminary analysis for sentinel cohort.

The secondary efficacy analysis will also be performed on the mFAS by injection group as actually received.

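### SAP 5.1 and 5.1.1.4 give different pooling rules for immunogenicity; read literally, 5.1 would mix one- and two-injection participants from D36 onward

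*SAP*

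**What the plan says.** SAP 5.1 (Statistical Methods) restricts immunogenicity and efficacy analyses to the combined Sentinel and Full Enrollment population, in which the same "dose-level group in Sentinel Cohort and Full Enrollment Cohort will be pooled".

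SAP 3.1 defines the larger cohort: "The Full Enrollment Cohort includes both Cohort 1 and Cohort 2". Cohort 1 participants "were to receive a single injection of study intervention while participants in Cohort 2" were to have two, 21 days apart. Sentinel participants were also to have two.

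SAP 5.1.1.4, on the primary immunogenicity objective, gives another rule: "The same dose-level group in Sentinel Cohort and Cohort 2 will be pooled for analysis". SAP 5.1.1.2 uses the same narrower rule for safety: "The same dose-level group in Sentinel Cohort and Cohort 2 will also be pooled for analysis". SAP 5.1.2.2, on secondary immunogenicity, has no pooling rule of its own.

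SAP 5.2.5 adds that the immunogenicity analyses "will be performed on the mFAS by injection group as actually received". It does not say whether injection group means dose, number of injections, or both.

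**The concern.** A programmer who follows 5.1 puts Cohort 1 into each dose-level group; one who follows 5.1.1.4 leaves it out. Both rules cover the primary immunogenicity endpoints. For secondary binding antibody only the 5.1 rule exists.

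At D36 a Cohort 1 participant is 35 days past a single injection, while a Sentinel or Cohort 2 participant is 14 days past the second. A GMT over both describes neither schedule. Fold-rise, the 2- and 4-fold-rise proportions and seroconversion at D36 are exposed in the same way, as are the later time points.

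A related gap lies in the undefined term in 5.2.5. Further vaccination was stopped on 27 September 2021 (SAP 1), so some Cohort 2 participants may have had only one injection. The mFAS, now used for immunogenicity, requires at least one injection and, unlike the PPAS, does not exclude incomplete schedules. Even under 5.1.1.4, then, a Cohort 2 group formed by assignment could hold one-injection recipients at D36. The documents do not say how many.

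**Working it through.** **Planned numbers.** Protocol Table 4.3 gives 44 per vaccine group and 22 per placebo group in each of Cohorts 1 and 2. Per cohort, 3 × 44 + 22 = 154. Two cohorts give 308, as stated. Adding 25 Initial Sentinel participants gives 333, and adding a fully expanded Sentinel Cohort of 75 gives 383; both match the protocol.

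**Group size per dose level under each rule**

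| Sentinel N at that dose | 5.1.1.4: Sentinel + Cohort 2 | 5.1 literal: Sentinel + Cohorts 1 and 2 | Single-injection share f under 5.1 |
|---|---|---|---|
| 25 (expanded) | 25 + 44 = 69 | 25 + 88 = 113 | 44/113 = 0.389 |
| 10 (initial only) | 10 + 44 = 54 | 10 + 88 = 98 | 44/98 = 0.449 |

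Under 5.1.1.4 all are planned for two injections, so f = 0.

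**Which time points are exposed.** The primary titre endpoint is "Neutralizing antibody titer on D01, D22, and D36". D01 precedes any injection. At D22 everyone has had one injection: the Sentinel schedule states that the "BL0002 sample will be collected prior to D22 vaccination", and the Cohort 2 schedule (Protocol Table 1.5) likewise places it before the second vaccination. Among the primary time points, only D36 can be mixed.

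**Effect on the D36 GMT.** Let G1 and G2 be the D36 GMTs after one and two injections, and R = G2/G1. The log of a pooled GMT is the weighted mean of the logs:

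log G(pooled) = f · log G1 + (1 − f) · log G2, so G(pooled)/G2 = R^(−f).

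The documents give no value for R; the range below is an assumption.

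| Group | f | R = 1 | R = 2 | R = 5 | R = 10 |
|---|---|---|---|---|---|
| All ages, Sentinel 25 | 0.389 | 100% | 76% | 53% | 41% |
| All ages, Sentinel 10 | 0.449 | 100% | 73% | 49% | 36% |
| ≥ 50 years (24 of 48; no Sentinel) | 0.500 | 100% | 71% | 45% | 32% |

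For example, 5^(−0.389) = 0.53 and 10^(−0.389) = 0.41. The older stratum is diluted most because no Sentinel participants add to its two-injection share.

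**The case against.** The strongest reply is that the rest of the SAP shows what is meant.

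- Section 5.1.1.4 governs the primary endpoints and names Cohort 2 explicitly; 5.1.1.2 does the same for safety.
- The regression text in 5.1.1.4 uses D22 for Cohort 1 and D36 for Sentinel and Cohort 2, and has injection schedule as a covariate.
- Table 5.2 maps unscheduled visits separately for one and two injections.
- Section 5.7 drops analyses by aggregated groups. Protocol 9.2 lists dose among the effects assessed by aggregating vaccine arms, so pooling a dose across schedules looks like an analysis of the dropped kind.
- The 5.1 sentence may be meant only to say who is analysed, in contrast to the safety sentence before it. The separate Tables, Listings and Figures document, which is not available here, may define the groups.

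This stands as evidence of intent. A reader might infer from 5.1 that the schedules will be mixed; the documents do not support that, only that one stated rule would mix them. But none of these passages amends the 5.1 sentence, supplies a rule for 5.1.2.2, or defines injection group.

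Two further inferences would go too far. One is that a dose or schedule choice is at risk: choosing them was a design purpose, but development has been discontinued, no hypotheses are tested on immunogenicity, and the between-group GMT ratios and seroconversion differences are dropped. The other is that the primary GMTs would be roughly halved. That needs an R of 5 to 10, which has no source in the documents, and it concerns D36 only.

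**Conclusion.** The two pooling rules conflict, and the SAP should be corrected. SAP 5.1 taken literally would mix one- and two-injection participants in the D36 and later immunogenicity summaries, primary and secondary, and by the same sentence in the descriptive efficacy counts. The narrower rule in 5.1.1.4 is probably the intended one.

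Any dilution of the D36 GMT runs from none at R = 1 to a pooled value 41% of the two-injection GMT at R = 10, taking 44 of 113 as single-injection. These figures rest on an assumed R and on planned numbers with a fully expanded Sentinel group. Enrollment stopped early, so the actual shares will differ. What remains at stake is that the reported GMTs describe an identifiable schedule.

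**What to change.** 1. In SAP 5.1, replace the pooling sentence: *for immunogenicity and efficacy, the same dose level is pooled across Sentinel and two-injection Full Enrollment participants only; one-injection participants are shown separately by dose level.*
2. In SAP 5.2.5, define injection group as actually received: *dose level received by number of injections received.*
3. Apply that one as-received definition in 5.1, 5.1.1.4 and 5.1.2.2, in place of pooling by assigned cohort. A Cohort 2 participant who had only one injection when vaccination stopped is then not counted in the two-injection group at D36 and later. Without this step the fix would contradict itself, because pooling by assigned cohort and grouping by injections received place that participant differently.

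The cost is a few sentences of SAP text and a check that the Tables, Listings and Figures document uses the same groups. No new data are needed and study conduct does not change. If tables are already programmed, confirm which rule was used.

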5.1.1 Hypotheses and Statistical Methods for Primary Safety Objective

5.1.1.1 Primary Safety Hypotheses

No hypotheses were tested.

5.1.1.2 Statistical Methods for Primary Safety Objective

The following safety parameters will be used for the evaluation of safety. Additional parameters may be displayed as appropriate.

Solicited Reactions

Number and percentage of participants with:

- Presence of solicited injection site reactions and systemic reactions occurring up to 7 days after injection
- Each solicited reaction according to time of onset, maximum intensity, and number of days of occurrence over the solicited period

Unsolicited Events and Reactions

Number and percentage of participants with:

- Any unsolicited immediate systemic event in the 30 minutes after injection
- Any unsolicited event and reaction (using the current MedDRA version) 21 days after injection
- Any unsolicited event/reaction according to time of onset, maximum intensity, and duration

SAEs

Number and percentage of participants with:

- Any SAE within 21 days after injection and throughout the entire study according to SOC and PT, seriousness, and outcome

AESIs

Number and percentage of participants with:

- Any AESI within 21 days after injection and throughout the entire study according to SOC and PT, seriousness, and outcome

MAAEs

Number and percentage of participants with:

- Presence of MAAEs within 21 days after injection and throughout the entire study

Laboratory tests

- Presence of out-of-range biological test results up to 8 days post-last dose (ie, up to D09 for Cohort 1 and up to D30 for Sentinel Cohort and Cohort 2)
- Summary of toxicity grade shift from baseline

For descriptive purposes, the statistics presented in [Table 5.1](#) will be produced for the above safety parameters for each intervention group and each age group. The same dose-level group in Sentinel Cohort and Cohort 2 will also be pooled for analysis.

Harm analysis

Harm analysis assessed based on split of COVID-19 case will be assessed based on Safety Analysis Set (SafAS) at the time of the final analysis. Participants will be analyzed according to the study intervention they received. For the assessment, all dose-level arms will be pooled, and all placebo arms will be pooled as well.

The assessment for COVID-19 will be implemented separately using a one-sided conditional exact binomial test of $H_0: p \leq \text{“number of participants in the pooled mRNA vaccine arm”} / \text{“total number of participants”}$ versus $H_1: p > \text{“number of participants in the pooled mRNA vaccine arm”} / \text{“total number of participants”}$, where p is the binomial probability that a case participant is assigned to the pooled mRNA vaccine group conditional on the observed total number of cases. The test will be performed at the same pre-specified one-sided nominal/unadjusted alpha-level of 0.05 (unadjusted). The bounds for harm monitoring are computed under the null hypothesis that $VE=0\%$.

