After the planned preliminary interim of the Sentinel Cohort participants, a decision to discontinue the development of the mRNA COVID-19 vaccine was made. On September 27, 2021, all Investigators were informed to terminate further vaccinations and enrollment. All enrolled participants were to be unblinded to allow them to make their decision to receive an authorized COVID-19 vaccine. All clinical sites were to contact participants to inform them of the discontinuation of further study vaccinations, told what intervention they received and invited to come in for an unscheduled visit for counseling to answer any questions about the study, to discuss available options for receipt of an approved /authorized COVID vaccination, and were requested to provide unscheduled blood draw for serological assessment (UBXX). Participants were informed that additional D22 or D36 blood draws for serological assessment would be appreciated but are not mandatory. No protocol defined schedule visits or blood draws at timepoints later than D36 were required. Monitoring for SAEs, AESIs, medically attended AEs, and pregnancy and collection of influenza and COVID-19 vaccines were continued with safety calls. On March 15, 2022, after concurrence from regulatory authorities, Investigators were notified of the decision to end the study at the 6-month safety follow-up instead of 12-month follow-up.

This version 5.0 of SAP is updated for the final unblinded analysis. The sections of Trial Objectives and Trial Design and Plan are kept the same with the final protocol, but modifications are made in Section 4 and Section 5 for endpoint derivation, statistical methods, and populations used in analyses, to reflect the changes needed for the final analyses.

2 Trial Objectives

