4.4.1.3 SAEs

SAEs will be analyzed throughout the study using the following periods:

- Within 21 days after each injection
- During the study (ie, all SAEs occurred during the entire study or the cutoff date which corresponds to the date of any interim analysis)

Note: SAE that occurred before vaccination (negative time of onset) will not be included in analysis but will be listed separately.

Main safety analysis will include only those SAEs with time of onset before a participant received a non-study authorized/approved COVID-19 vaccine, if applicable. SAEs with time of onset on or after the date of receiving a non-study authorized/approved COVID-19 vaccine will be listed separately.

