4.4.1.5.7 AESI

AESIs will be collected throughout the study to ensure that events are communicated to the Sponsor in an expedited manner and followed-up until the end of the follow-up period or resolution, as per the assigned causality.

AESIs will include:

- Protocol-specified AESIs: Anaphylactic reactions, generalized convulsions, Guillain-Barré Syndrome (GBS), acute disseminated encephalomyelitis (ADEM), thrombocytopenia, and vasculitides
- New-onset chronic medical conditions (NOCMCs)
- AESIs related to SARS-CoV-2 infection and COVID-19 disease (see Appendix 10.5 of the protocol).

NOCMCs are defined as any new ICD-10 diagnosis (10th revision of the International Statistical Classification of Diseases and Related Health Problems) that is applied to the participant during the course of the study, after receipt of the study agent, that is expected to continue for at least 3 months and requires continued health care intervention.

AESIs will be analyzed throughout the study using the following periods:

- Within 21 days after each injection
- During the study (ie, all AESIs occurred during entire the study or the cutoff date which corresponds to the date of any interim analysis)

Note: AESI with time of onset before first vaccination (negative time of onset) will not be included in analysis but will be listed separately.

Main safety analysis will include only those AESIs with time of onset before a participant received a non-study authorized/approved COVID-19 vaccine, if applicable. AESIs with time of onset on or after the date of receiving a non-study authorized/approved COVID-19 vaccine will be listed separately.

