4.4.5.3 Participant Duration

The duration of a participant participation in the study is computed as follows:

Maximum (Visit dates, Termination date, contact dates) – V01 date + 1

5 Statistical Methods and Determination of Sample Size

The statistical analyses will be performed under the responsibility of the Sponsor’s Biostatistics platform using SAS® Version 9.4 or later.

The results of the statistical analysis will be available in the final clinical study report (CSR).

For descriptive purposes, the following statistics will be presented as shown in [Table 5.1](#).

Table 5.1: Descriptive statistics produced

Baseline characteristics and follow-up description	Categorical data	Number of participants. Percentage of participants and 95% CI.
	Continuous data	Mean, standard deviation, quartiles, minimum, and maximum.
Clinical safety results	Categorical data	Solicited: Number and percentage (95% confidence intervals [CIs]) of participants. Unsolicited: Number and percentage (95% CIs) of participants, and number of events.
Immunogenicity results	Categorical data (seroconversion, 2 fold-rise, 4 fold-rise)	Number and percentage (95% CIs) of participants.
	Continuous data (titer / data)	Anti-Log ₁₀ (work on Log ₁₀ distribution, and anti-Log ₁₀ applied): Geometric mean, 95% CI of the geometric mean, quartiles, minimum, and maximum. Graphical representation by Reverse Cumulative Distribution Curve (RCDC).
Efficacy results	Categorical data	Number and percentage (95% CIs) of participants.

The CI for the single proportion will be calculated using the exact binomial method (Clopper-Pearson method, quoted by Newcombe (4), ie, using the inverse of the beta integral with SAS®).

For immunogenicity results, assuming that Log₁₀ transformation of the titers / data follows a normal distribution, at first, the mean and the 95% CI will be calculated on Log₁₀ (titers / data) using the usual calculation for normal distribution (using Student's t distribution with n-1 degree of freedom), then antilog transformations will be applied to the results of calculations, in order to provide geometric means (GMs) and their 95% CI.

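### Whole-study SAE, AESI and MAAE percentages take no account of time at risk, although events are cut at an outside COVID-19 vaccine chosen after unblinding

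*SAP*

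**What the plan says.** SAP 5.1.1.2 asks for the number and percentage of participants with each event type. For SAEs this is "Any SAE within 21 days after injection and throughout the entire study according to SOC and PT, seriousness, and outcome"; AESIs are worded the same way, and MAAEs are "Presence of MAAEs within 21 days after injection and throughout the entire study". Table 5.1 in SAP Section 5 sets the statistics: "Unsolicited: Number and percentage (95% CIs) of participants, and number of events". The interval method is also fixed there: "The CI for the single proportion will be calculated using the exact binomial method", that is, Clopper-Pearson.

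The numerator is cut. SAP 4.4.1.3 states: "Main safety analysis will include only those SAEs with time of onset before a participant received a non-study authorized/approved COVID-19 vaccine, if applicable". SAP 4.4.1.5.7 has the same rule for AESIs and 4.4.1.5.8 for MAAEs. Later events are listed, not tabulated. Participants with no outside vaccine contribute safety data up to their last phone contact (SAP 5.1).

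The denominator is not cut. The Safety Analysis Set in SAP 5.2.2 holds everyone who received at least one injection.

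SAP Section 1 and SAP 5.7 describe what came before many of these cut-offs: "All enrolled participants were to be unblinded to allow them to make their decision to receive an authorized COVID-19 vaccine". Investigators were informed on 27 September 2021, and follow-up was later shortened from 12 to 6 months.

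**The concern.** Each participant is observed for as long as it takes to reach an outside vaccine or the last contact, but counts as one full binomial unit whatever that time is. The SAP recognises the problem for other variables: 4.4.1 describes the main analysis of selected endpoints as censored at the outside vaccine, and 4.4.1.2.2 and 4.4.1.2.5 set intensity and duration to missing when an unsolicited event runs past it. The whole-study percentages have no matching adjustment.

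The cut-off is not a neutral date. After unblinding it follows a decision made with knowledge of the arm, so observed time could differ between vaccine and placebo groups. Protocol 4.2 gives safety comparison with placebo as a reason for having that arm, and SAEs, AESIs and MAAEs throughout the study are primary safety endpoints (Protocol Table 3.1). A reader who sets the columns side by side cannot tell a difference in risk from a difference in observed time.

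**Working it through.** **1. The plan's own figures.** The documents state no power, event rate or exposure figure for this point; the only figures to reproduce are the denominators. From Protocol Table 1.2, the Full Enrollment Cohort is 2 × (3 × 44 + 22) = 308, of whom 2 × 132 = 264 are on vaccine and 2 × 22 = 44 on placebo. With 25 Initial Sentinel participants the total is 333; with 75 Sentinel participants the maximum is 383. All three totals agree with the protocol.

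**2. Assumptions.** Uptake of outside vaccine, its timing by arm and the event rates are not in the documents. I assume a 6-month risk R of 2% to 30% and 2 to 6 months observed. With a constant hazard λ = −ln(1 − R)/6 per month, the crude percentage after t months is 1 − exp(−λt).

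**3. Equal hazards, R = 20%.** λ = −ln(0.8)/6 = 0.0372 per month.

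| Months observed (vaccine vs placebo) | Crude % | Ratio |
|---|---|---|
| 6 vs 6 | 20.0 vs 20.0 | 1.00 |
| 6 vs 5 | 20.0 vs 17.0 | 1.18 |
| 6 vs 4 | 20.0 vs 13.8 | 1.45 |
| 6 vs 3 | 20.0 vs 10.6 | 1.89 |
| 6 vs 2 | 20.0 vs 7.2 | 2.79 |
| 3 vs 6 | 10.6 vs 20.0 | 0.53 |

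At 6 vs 3 months and R of 2%, 10%, 20% and 30%, the ratios are 1.99, 1.95, 1.89 and 1.84, and the differences 1.0, 4.9, 9.4 and 13.7 percentage points. For rare events such as SAEs the ratio is distorted about as much, but the absolute gap is small.

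**4. Masking.** With a true hazard ratio of 2, a placebo 6-month risk of 20%, and vaccine observed for 3 months against 6 for placebo, the vaccine percentage is 1 − exp(−2 × 0.0372 × 3) = 20.0% and the placebo percentage is 1 − exp(−0.0372 × 6) = 20.0%. The doubled hazard does not show.

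**5. Would a simple person-time rate cure this?** Only if the hazard is constant. Suppose both groups have a hazard of 0.15 in month 1 and 0.02 per month afterwards, observed for 6 vs 2 months.
- Cumulative hazards: 0.15 + 5 × 0.02 = 0.25, and 0.15 + 0.02 = 0.17.
- Crude percentages: 1 − exp(−0.25) = 22.1% and 1 − exp(−0.17) = 15.6%, ratio 1.41.
- Average rates: 0.25/6 = 4.2 and 0.17/2 = 8.5 per 100 person-months, ratio 0.49.
- Cumulative incidence read at the common time of 2 months: 15.6% in both, ratio 1.00.

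The rate errs further than the crude percentage, and in the other direction. An estimate that censors at the cut-off and is read at the same time in each group does not have this fault.

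**6. Safeguards elsewhere.** Participant duration (SAP 4.4.5.3) runs to the last visit, termination or contact, not to the outside vaccine, so it overstates time at risk for anyone who switched. SAP 5.7 lists complementary and sensitivity analyses of safety data among those not performed.

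**The case against.** There is a fair case that little is lost.

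- Safety reporting is descriptive. Protocol 9.1 and SAP 5.1.1.1 test no safety hypothesis, and the only test in SAP 5.1.1.2 concerns the split of COVID-19 cases. The objective is to describe each group. This stands: no error rate is at issue, only how side-by-side results are read.
- SAEs, AESIs and MAAEs are also tabulated within 21 days of each injection, where long-term follow-up matters little, and later events are listed rather than lost. This stands.
- SAP 5.1 has a safety population restricted to the Full Enrollment Cohort, with pooling added if necessary. The contrast with placebo can therefore be read without Sentinel data. This stands.
- SAP 5.1.1.2 allows additional parameters, and the separate tables, listings and figures document is not available here. Exposure displays may exist there, but nothing in the SAP commits to them.
- The groups are small. With 22 placebo participants per schedule, 3/22 = 13.6% has a Clopper-Pearson interval of 2.9% to 34.9%. Chance may outweigh the effect described, but such an interval does not reflect unequal observation time.

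A reader might infer that placebo recipients switched sooner, so that their window was shorter. The documents do not show this. All participants, vaccine recipients included, were told that study vaccination had stopped and were invited to discuss authorized vaccines, so times may have been similar. A reader might also infer longer windows in the Sentinel Cohort because it enrolled first. Earlier entry alone does not lengthen a participant's window when the study ends at the 6-month follow-up. The notice of 15 March 2022 leaves longer windows possible, but no figures are given.

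**Conclusion.** The point holds in conditional form. Whole-study SAE, AESI and MAAE percentages count events only up to an outside vaccine, keep every injected participant in the denominator, and come with no specified account of time at risk. If time to cut-off differs between groups, equal risks can give unequal percentages or a real excess can be masked. The sizes in the working, such as 20.0% versus 10.6% at 6 versus 3 months, rest on an assumed constant hazard and assumed months; actual direction and size are unknown.

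The documents do not support the stronger conclusion that the percentages reflect follow-up length rather than risk, since observed time could turn out similar. What can be said is that the specified tables do not let a reader judge this. It is worth correcting because safety comparison is a stated purpose of the placebo arm and the correction is cheap.

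**What to change.** Keep the percentages and the 21-day tables. In SAP 5.1.1.2 add, for each intervention group, with the Full Enrollment Cohort shown separately from any pooling with Sentinel:

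1. The distribution of time from first injection to the earlier of outside COVID-19 vaccine or last contact.
2. For first SAE, first AESI and first MAAE, the Kaplan-Meier cumulative incidence with 95% CI at common time points, censoring at outside vaccine or last contact. Fix the time points in the SAP before the tables are run, and show the numbers still at risk.

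Optionally add first-event incidence per 100 person-months, with person-time ending at the first event, outside vaccine or last contact, and an exact Poisson 95% CI. State that it assumes a constant rate.

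Cost: a paragraph in the SAP and a little programming. No new data are needed: first-visit and contact dates are already used in SAP 4.4.5.3, and outside COVID-19 vaccination is collected throughout (Protocol 6.5). Limitation to state with the results: neither summary removes bias if the decision to take an outside vaccine is related to health.
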